### **2.3.2 Experience in Dialysis Patients**

Two Phase 2 trials, 1 in Poland (CLN-PRO-V001) and 1 in the United States (US) (CLN-PRO-V003) have completed enrollment. Both recruited subjects requiring hemodialysis access for end-stage renal disease whom were not suitable for creation of an AVF. Most subjects had undergone previous vascular access procedures, in many cases multiple attempts including both AVFs and synthetic grafts. Initial results from these Phase 2 studies are discussed below.

The primary objectives of these 2 studies are to evaluate both the safety of HAV and its efficacy in terms of primary and secondary patency at 6 months. Secondary objectives include measurement of a PRA response, development of IgG antibodies to the extracellular matrix material in the HAV and a 2 year evaluation of patency and an assessment of the need for interventions to maintain/restore patency. Follow up has now been extended up to 120 months.

A phase 3 randomized study comparing HAV with expanded PTFE (ePTFE) grafts (CLN-PRO-V006) has completed enrollment in the US, Europe, and Israel. A second phase 3 randomized study (CLN-PRO-V007) comparing HAV with AVF is currently enrolling in the US. As the sponsor is blinded, no efficacy information currently available for the phase 3 studies; however, blinded safety data is presented in the Investigator Brochure.

#### **2.3.2.1 CLN-PRO-V001 and CLN-PRO-V003 Study Results (24 M)**

All subjects (n = 60) have now completed at least 24 months since implantation (or had a censoring event). The first subjects recruited are now beyond 60 months after HAV implantation, some with functioning HAV for hemodialysis access. Together these 2 trials provide more than 150 years of follow up during which the HAV has been used for more than 15,000 hemodialysis sessions.

When HAV thrombosis has occurred it has almost always been managed successfully, often allowing immediate resumption of dialysis without the need for the placement of a dialysis catheter. One non-serious arteriovenous graft aneurysm was reported in Study CLN-PRO-V001 (moderate in intensity, considered possibly related to IMP and considered not related to procedure – this patient died before the Sponsor could complete the follow up of this event). An expected number of small pseudoaneurysms have been observed, which is consistent with all surgically-created hemodialysis access. Most have resolved spontaneously with only 2 cases requiring surgical intervention. Flow rates through the HAV were more than sufficient to allow for effective dialysis.

In both studies, the product has generally been well tolerated and blood chemistry, hematology and coagulation data are not indicative of any HAV-associated toxicity. Immunogenic response to the HAV material has not been observed as demonstrated by a general lack of HAV-related change in PRA levels (Class I or II). Three subjects had elevations in their PRA levels: all 3 subjects had experienced 1 or more renal transplant failures; 1 subject recently; 1 subject developed septic shock about a month before the elevated value; and the third subject, who

was severely debilitated with a decubitus ulcer, died approximately a month after HAV abandonment.

IgG titers increased in 5 subjects; in 4 cases the IgG titer increased and then decreased while the HAV remained functional with no clinical evidence of an inflammatory response; in 1 case the IgG titer increase occurred in a subject who maintained primary patency.

Adverse events (AEs) related to the HAV/access site (excluding thrombotic events) were few; there have been only 3 access-site infections, of which only 1 required removal of part of the HAV. There have been:

- 1 kidney transplant (known to be functioning well at 12 months post-transplant)
- 15 deaths, all after abandonment or during follow-up; none of the deaths were considered related to the presence of the HAV

Patency data for the 2 studies in dialysis access has been pooled for a combined Kaplan-Meier (K-M) analysis ([Lawson, 2016](#)). Based on these K-M plots the patency at 6, 12 and 24 months is estimated to be 60%, 26% and 15% (primary patency) and 97%, 91% and 77% (secondary patency).

### **2.3.3 Experience in Peripheral Arterial Bypass Patients**

Humacyte has 2 Phase 2 studies to assess the safety and efficacy of the HAV when used as an above-knee arterial bypass graft. The first study, CLN-PRO-V002, is a single group uncontrolled study conducted at 3 sites in Poland that is fully enrolled and in long-term follow up. Eligible patients required a femoro-popliteal bypass graft for the management of symptomatic peripheral arterial disease. Pre-operative imaging (conventional or computed tomography [CT] angiography) must have demonstrated at least 2 below knee vessels patent to the ankle with good runoff. The proximal anastomosis was expected to be below the inguinal ligament and the distal anastomosis above the knee. Autologous vein grafts must not have been suitable or feasible (e.g., because of severe venous disease or prior use of leg veins for other bypass surgery or there is a clinical need to preserve those veins for future bypass surgery in the coronary or peripheral circulation).

The HAV was implanted using standard vascular surgical techniques and the patency of the bypass confirmed by intraoperative angiography (conventional or intra-op CT angiography) or ultrasound. The patient was then followed up at study visits at 15 days, 6 weeks and 3, 6, 12, 18 and 24 months. At each visit safety was assessed by clinical examination and adverse events, and the HAV was examined using duplex ultrasound to visualize the entire length to confirm patency, flow and to detect stenosis, aneurysm development or dilatation.

The primary objectives of the study are to evaluate the safety and tolerability of the Humacyte HAV in PAD patients undergoing above-knee femoro-popliteal bypass surgery and to determine the patency (primary, primary assisted and secondary) rate of the Humacyte HAV at 24 months. Secondary objectives include assessment of the PRA and IgG response to the HAV and to

assess patency (primary, primary assisted and secondary) at 6, 12 and 18 months, to determine the rates of interventions needed to maintain/restore patency in the HAV, to assess any effect of implantation on claudication, rest pain and ischemic ulcers and to assess any effect on ankle-brachial index (ABI).

The second PAD study of similar design, CLN-PRO-V004, is being conducted in the US with enrollment ongoing.

### **2.3.3.1 CLN-PRO-V002 Study Results (24 M)**

Recruitment began in October 2013 and was completed in June 2014 with 20 patients implanted. Thirteen patients completed the 2 year follow up visit. Of the 7 patients terminating the study early, 3 died and 4 were withdrawn after occlusion of the HAV. None of the deaths were considered related to the investigational device or procedure.

Kaplan-Meier analyses in which deaths were censored revealed primary, primary assisted, and secondary patency probability rates of 79.2%, 79.0%, and 89.5% at Week 26, 63.3%, 63.2%, and 84.2% at Month 12, 63.3%, 63.2%, and 79.0% at Month 18, and 58.1%, 57.9%, and 73.7% at Month 24.

Six patients (30%) required at least 1 graft intervention to maintain or restore HAV patency during the study. Four patients required 1 intervention and 1 patient each required 3 and 4 interventions. Most interventions successfully restored patency. However, in 1 patient the graft patency could not be restored and the HAV was replaced with an alternative bypass graft. Two patients, who had previously undergone successful interventions, developed a recurrent thrombosis which was not treated and the HAV was left occluded. Two patients experienced HAV thrombosis with no or minimal symptoms and refused interventions on the HAV.

All 20 patients experienced AEs (a total of 92 events). Thirty-one of these events in 13 patients were considered serious. The most frequent AEs reported included graft thrombosis (35% of patients), anastomotic stenosis (20% of patients), lymphocele (20% of patients), and local swelling (15% of patient). Those serious adverse events (SAEs) reported by at least 2 patients were graft thrombosis (6 patients, 30%) and anastomotic stenosis (2 patients, 10%).

No patient showed an increase in PRA levels. Two patients had a significant (> 2 fold) increase from baseline in IgG levels. One of these patients experienced a thrombosis of the HAV between 3 and 6 months after implantation, while the other patient has had no HAV-related AEs and continues to have primary patency. Neither patient has had any evidence of dilatation or structural degeneration of the HAV.

### **2.3.4 Human Acellular Vessel Host Response and Remodeling Data**

Humacyte has been able to assess the general host response to the HAV in a number of human participants; this was accomplished through the microscopic examination of explanted HAV and adjoining tissue samples obtained during surgical revision procedures in 8 cases. The analysis (mostly of a section close to the venous anastomosis) included assessments of:

- Cellular infiltration of histotypic, inflammatory and immunological populations.
- Extracellular remodeling processes, including neo-synthesis and reorganization of ECM components that typically occur in native blood vessels.

[figure not shown]
In these cases, small segments of the HAV and adjacent vascular tissue were explanted, fixed in formalin solution and shipped to Humacyte for analysis. Implant duration ranged from 16 to 55 weeks (median: 37 weeks).

In man, the HAV remodeled in a manner consistent with that observed in primate studies. There was infiltration of cell populations that are normally associated with angiogenesis and vascular organization and structure; namely, those with endothelial, smooth muscle and fibroblastic phenotypic characteristics were observed. Endothelial cells formed a monolayer on the luminal surface of the HAV. Migration of actin-positive smooth muscle cells into the wall of the HAV was consistently observed. A well-vascularized adventitial layer of non-constrictive fibrous tissue formed around HAV. Infiltration of the graft material by inflammatory and immunoreactive cell populations was either not evident or was mild and generally unremarkable. Degradation or breakdown of the implant was not observed.

Histotypic neo-synthesis and reorganization of the ECM was observed in patterns indicative of integration of the HAV into the host. An increase in the density of collagen type I, the main type of collagen found in the wall of native blood vessels, was apparent in the majority of HAV explant specimens. The structure of collagen type I in these specimens exhibited a more mature, organized pattern, with distinct fibers and a prominent circumferential alignment evident in explanted samples in comparison with pre-implant specimens. In some specimens, the fibrillar staining pattern of collagen III became more prominent and more organized, with a circumferential orientation. Fibronectin levels and staining patterns remained unchanged.

Cannulation sites within the HAV appeared to be repaired by the host in a fashion similar to wound repair in the body ([Figure 1](#)). In 1 case, an explanted specimen was tested for suture retention strength at the time of explant and exhibited a substantial increase over the pre-implant level.

**Figure 1** Images of Mid-Vessel Segment Explanted at 11-Months Post-Implant

- A: Low magnification showing 3 cannulation sites (in dashed boxes),
- B: Fresh cannulation track,
- C: Cannulation track during remodeling
- D: Older cannulation track that has been repaired.

The images above show a mid-vessel segment explanted at 11 months post-implant, and shows several prior cannulation tracts from dialysis access. Section B shows a very recent cannulation site with fresh clot extending into the tract from the lumen. Sections C and D show partially healed cannulation tracts, with evidence of cellular repopulation extending in from the lumen. Remodeled cannulation tracks contain new collagen and a few micro-conduits.

In conclusion, the HAVs were remodeled by the host to form a vascular-like structure more similar to the histological appearance of native vasculature. The HAVs were repopulated by cell types that are characteristic of healthy native vasculature. Evidence of ECM remodeling processes, including neo-synthesis and reorganization of ECM components that typically occur in native blood vessels, were observed. The cellular infiltration and ECM remodeling patterns were indicative of the integration of the HAV into the host.

### 2.3.5 Conclusions

Clinical experience indicates that the HAV remains mechanically strong over implantation periods of more than 60 months with no evidence of dilatation. During more than 200 patient years of follow up across the 3 Phase 2 studies only 1 case of infection of the HAV material

itself has been reported. The SAE profile has been typical of that expected in the dialysis and PAD populations. In hemodialysis populations, secondary patency of the HAVs is substantially higher than the historical data for both ePTFE and AVF (accounting for non-maturation). In PAD, patency is in line with historical ePTFE and autologous conduit for above knee bypass. No evidence of immunogenicity of the HAV has been found and the HAV remains mechanically robust even after repeated puncture for hemodialysis and under high pressure, high outflow resistance in arterial reconstruction.

These data support the use of HAV in future Phase 2 and phase 3 studies for vascular replacement and reconstruction in diseased or damaged (trauma) vessels.

## **2.4 Study Design Rationale**

Previous studies with the HAV have used IMP manufactured using small-scale systems (Aura and Terra). Prior to commercialisation, manufacturing has been switched to a larger-scale automated process with greater in-process controls (Luna). Based on a large number of preclinical parameters, including those used for batch release, the IMP manufactured using the Luna system is comparable to that used in earlier clinical studies. This study will allow confirmation of the short-term safety, efficacy and absence of immunogenicity of the Luna product.

Any significant safety or immunogenicity concerns with the HAV would likely be apparent in a short time frame after implant. Thus, the initial study analysis will be conducted after all subjects have reached 3 months post-implant. However, all subjects will be followed for 12 months and those with a patent HAV will continue follow up to 36 months to monitor for any potential long-term safety concerns with the Luna product.

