## Protocol Summary

Full Title	A Phase 2 Assessment of Humacyte's Human Acellular Vessel in Patients Needing Vascular Access for Dialysis
Clinical Trial Phase	Phase 2
Sponsor	Humacyte, Inc.
Planned Study Sites	2 sites in Poland
Sample Size	Up to 30 patients implanted with a Human Acellular Vessel (HAV)
Expected Enrollment Start	2Q 2019
Study Rationale	Previous studies with the HAV have used Investigational Medicinal Product (IMP) manufactured using small-scale systems (Aura and Terra). Prior to commercialisation, manufacturing has been switched to a larger-scale automated process with greater in-process controls (Luna). Based on a large number of preclinical parameters, including those used for batch release, the IMP manufactured using the Luna system is comparable to that used in earlier clinical studies. This study will allow confirmation of the short-term safety, efficacy and absence of immunogenicity of the Luna product.
Study Population	Subjects with end-stage renal disease (ESRD) who require hemodialysis and are targeted for implantation of an arteriovenous (AV) graft for dialysis access.
Enrollment Period	2 months
Study Duration	Each subject will be followed by study specific visits until he/she completes 1 year (12 months) of follow-up after implantation (irrespective of patency status). After 1 year, only subjects with a patent HAV will be followed (while the HAV remains patent) for up to 3 years (36 months) post-implantation at study visits every 6 months. The expected duration of the clinical investigation is 41 months (initiation of enrollment through completion of data collection).
Study Design	Prospective, two center, open-label, single-arm study.
Intervention Description	The IMP is Humacyte's HAV, which is a tissue-engineered vascular conduit for hemodialysis access. HAVs for this study will be manufactured using the Luna commercial manufacturing system.  Subjects will be implanted with an HAV in the forearm or upper arm

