### **3. INVESTIGATIONAL PLAN**

#### **3.1 Study Design**

This is a Phase 2, prospective, multicenter, open-label, single-arm study. Previous studies with the HAV have used Investigational Medicinal Product (IMP) manufactured using small-scale systems (Aura and Terra). Prior to commercialization, manufacturing has been switched to a larger-scale automated process with greater in-process controls (LUNA). Based on a large number of preclinical parameters, including those used for batch release, the IMP manufactured using the LUNA system is comparable to that used in earlier clinical studies. This study will allow confirmation of the short-term safety, efficacy and absence of immunogenicity of the LUNA product.

Up to 30 subjects who meet the inclusion/exclusion criteria specified in the Protocol, Section 5.1 will receive a HAV and will be followed to 12 months post-implantation at routine study visits regardless of patency status. After 12 months, subjects with a patent HAV will be followed (while the HAV remains patent) for up to 3 years (36 months) post-implantation at study visits every 6 months. See Appendix A for visit schedule.

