#### **4. GENERAL CONSIDERATIONS FOR DATA ANALYSIS**

CTI Clinical Trial and Consulting Services will perform all efficacy and safety statistical analyses described in this SAP. Any change to the data analysis methods described in the protocol will require an amendment of this SAP only if it changes a principal feature of the protocol. Any other change to the data analysis methods that are described in the protocol, and the justification for making the change, will be described in the clinical study report. Additional exploratory analyses of the data will be conducted as deemed appropriate.

The analyses for this study will be performed as follows:

- The primary analysis will be performed after the last subject completes 3 months of follow-up.
- A second analysis will be performed after all subjects have completed 12 months of follow-up.
- A final analysis will be performed after the last subject completes 36 months of follow-up.
- Interim safety data will be provided periodically to the Data Monitoring Committed (DMC) as per the DMC Charter.

A soft database lock will be required for the data included in the planned primary (3 months) and second (12 months) analyses. A final hard lock will be required for the final analysis at 36 months.

Statistical analyses will be primarily descriptive in nature. Unless otherwise specified, continuous variables will be summarized by presenting the number of non-missing observations, mean, standard deviation, median, inter-quartile range, minimum and maximum. Categorical variables will be summarized by presenting the number of subjects and percentage for each category.

All tabulations will be based on pooled data across centers.

Analyses will be performed using SAS for Windows statistical software, version 9.4 or higher (SAS, Cary, NC), except where other software may be deemed more appropriate.

Subject data will be listed and sorted by subject number.

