## **9. SAMPLE SIZE DETERMINATION**

This is an exploratory study with no formal hypothesis testing. No formal sample size estimates were performed. The number of subjects planned for this study is consistent with trials of this design and objectives.

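### The rationale promises confirmation of safety and of absent immunogenicity, but up to 30 subjects described without intervals on the safety event results can only support estimation

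*Protocol*

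**What the plan says.** Protocol 2.4 says of the trial: "This study will allow confirmation of the short-term safety, efficacy and absence of immunogenicity of the Luna product". The same sentence stands in the synopsis and in Protocol 2.1.2, and SAP 3.1 repeats it: "This study will allow confirmation of the short-term safety, efficacy and absence of immunogenicity of the LUNA product".

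The rest of the plan is more modest:

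- The primary objective (Protocol 3.1, SAP 2.1.1) is to evaluate safety, efficacy and immunogenicity over 3 months.
- The synopsis and Protocol 10 plan descriptive statistics only, with no hypothesis test. The synopsis caps enrolment at 30 implanted subjects without fixing a number.
- SAP 9 adds: "No formal sample size estimates were performed". No margin, upper limit or antibody responder definition is given.

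On uncertainty, SAP 6.1 provides 95% confidence intervals for Kaplan-Meier patency, and SAP 6.2 carries that method to 36 months. For everything else the default in SAP 4 applies: "Categorical variables will be summarized by presenting the number of subjects and percentage for each category", with mean, standard deviation, median, quartiles and range for continuous variables. SAP 7.2.5 and 7.2.6 give numbers, percentages and rates per 100 person-years, and SAP 7.3 gives raw and change-from-baseline laboratory summaries. None of these has an interval.

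On earlier experience, Protocol 2.3.2.1, which covers 60 dialysis subjects, reports "IgG titers increased in 5 subjects". Protocol 2.3.3.1, on 20 implanted bypass patients, reports "Two patients had a significant (> 2 fold) increase from baseline in IgG levels". Protocol 2.3.5 nevertheless concludes: "No evidence of immunogenicity of the HAV has been found".

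**The concern.** Confirming that something is absent needs a stated limit that the data must rule out, and a sample large enough to rule it out. The plan has neither, so the sentence gives the trial a property that its design does not have. The term immunogenicity is also undefined. The protocol reports antibody rises with earlier vessels and still concludes that no immunogenicity was found, so a reader cannot tell which result would count for or against absence.

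The missing safety intervals make this worse. The 3-month report carries interpretations and goes to regulators (Protocol 12), and it concerns a manufacturing change made before commercialisation. A bare 0 or 0% for rupture or infection, next to a rationale that speaks of confirmation, can look stronger than it is. The descriptive design does not explain the omission, because SAP 6.1 presents the patency intervals as descriptive statistics.

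**Working it through.** The documents give no power, precision or margin figure, so there is none to reproduce. The question is what up to 30 subjects can show.

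**1. Zero events among n subjects.** The exact two-sided 95% upper limit is 1 − 0.025^(1/n).

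| n | Upper limit for 0/n |
|---|---|
| 30 (planned ceiling) | 11.6% |
| 25 (assumed) | 13.7% |
| 20 (assumed) | 16.8% |

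The one-sided 95% bound for 0/30 is 1 − 0.05^(1/30) = 9.5%.

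**2. Small non-zero counts (Clopper-Pearson).** 1/30 = 3.3% (0.1% to 17.2%); 2/30 = 6.7% (0.8% to 22.1%); 3/30 = 10.0% (2.1% to 26.5%).

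**3. Earlier IgG rises, from Protocol 2.3.2.1 and 2.3.3.1.** Dialysis: 5/60 = 8.3% (exact 95% interval 2.8% to 18.4%). Bypass: 2/20 = 10.0% (1.2% to 31.7%). Both point estimates lie below 11.6%, so even 0/30 would not exclude them at the two-sided level. The one-sided bound of 9.5% would exclude 10.0% but not 8.3%.

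**4. Rare mechanical events.** The chance of seeing none in 30 is (1 − p)^30. For assumed true risks of 1%, 2% and 5% it is 74%, 55% and 21%.

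**5. Rates at the 3-month analysis.** The documents give no person-years, so these are assumptions:

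- 30 subjects with 3 months each: 30 × 3/12 = 7.5 person-years.
- 30 subjects enrolled uniformly over the planned 2 months, with all data included when the last reaches Month 3, so 4 months on average: 30 × 4/12 = 10 person-years.

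For zero events the exact Poisson upper limit is −ln(0.025)/T = 3.689/T.

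| Person-years | 0 events: upper limit per 100 | 1 event: rate per 100 (95% interval) |
|---|---|---|
| 7.5 | 49.2 | 13.3 (0.3 to 74.3) |
| 10 | 36.9 | 10.0 (0.25 to 55.7) |

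SAP 7.2.6 stops exposure at abandonment, transplant, termination or death, so actual exposure could be smaller and the limits wider.

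**6. Antibody endpoint.** The primary endpoint is change from baseline in PRA and anti-HAV IgG at 2 months (Protocol 4.2.1.1, SAP 2.2.1.1), summarised under SAP 7.3 as a continuous value with its dispersion. The binomial limits in steps 1 to 3 apply to it only once a subject can be classed as a responder or not, and the plan defines no such class.

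**The case against.** The strongest reply is that one loose sentence in a rationale is being read as the trial's aim. The objective says evaluate, the study is openly exploratory, and there is no decision rule to corrupt. Where a count and a denominator are tabulated, any reader can compute an exact interval. Much of this stands: the fault is a mismatch between wording and analysis, not a failed power calculation. It does not dispose of the point, because the sentence appears four times across two documents and the SAP prints intervals for efficacy but not for safety.

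A reader might infer more than the documents support:

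- *That 0/30 will be reported as proof of safety, or that one or two IgG rises would defeat the trial.* Neither document says so. Protocol 2.3.2.1 rests its no-response statement on PRA. It describes 4 of the 5 dialysis IgG rises as later falling, with a functioning vessel and no clinical inflammation; the fifth subject kept primary patency. In that usage, isolated titre rises need not contradict absence.
- *That a comparable product would almost surely show a rise.* Applying 5/60 to 30 subjects gives 1 − (55/60)^30 = 92.6%, but those rises come from a 24-month results section and the endpoint is at Month 2. If half appeared by then the figure would be 72.1%, and the half is itself a guess.
- *That earlier vessels caused PRA rises in 3 of 60 subjects.* The protocol does not attribute them to the vessel: all three had earlier transplant failures, and other illness is described. It reports no PRA increase in the bypass study.
- *That every primary safety endpoint is a bare count or rate.* Antibody change is continuous and is reported with its spread.

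**Conclusion.** The rationale sentence is wrong as written and should be changed, and the safety event results should carry intervals. This is a should-fix: no data, endpoint, sample size or decision rule is affected, and the trial's validity as an exploratory study is not in question.

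The binomial result depends only on the number of implanted subjects: at the planned ceiling, zero events is compatible with true frequencies up to 11.6%, and more with fewer subjects. The comparison with earlier IgG rises is looser. The 60 and 20 are study denominators, the numbers with IgG results are not given, the more than 2-fold cut-off is stated only for the bypass study, and the Month 2 frequency may be lower than either figure. The person-year limits rest on the two exposure assumptions shown.

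**What to change.** 1. **Synopsis, Protocol 2.1.2 and 2.4, SAP 3.1.** Say that the study will estimate safety, efficacy and immunogenicity in the short term, and drop both the claim to confirm and the word absence.
2. **SAP 7.2.6.** Add exact Clopper-Pearson 95% intervals for the primary safety event proportions: each mechanical-failure event, any mechanical-failure event per subject, and HAV infection. Some rows must be created. Abnormal post-cannulation hemostasis and the any-event row are not listed there, and infection is planned only as a rate. Add exact Poisson 95% intervals to the rates per 100 person-years. Intervals on every adverse-event row of SAP 7.2.5 are not needed.
3. **SAP 7.3.** Keep the continuous change-from-baseline summary for PRA and IgG and add a 95% interval. Report a responder proportion with an exact interval only after a PRA and IgG responder definition is pre-specified. The more than 2-fold IgG criterion in Protocol 2.3.3.1 is one candidate already in the documents.
4. **SAP 9.** State the precision: 0/30 excludes true frequencies above 11.6%, and fewer subjects exclude less.

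The cost is some wording, one definition and a few table rows and columns, with no new subjects, visits or samples. The stated conclusion becomes less favourable.
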